**Amendment 1 Rationale**

This amendment was made in response to regulatory agency feedback. Additional changes were made to correct errors and to provide additional clarity.

Major revisions include:

- Labeled safety objectives and endpoints as primary (Sections 1 and 4).
- Added a requirement for participants who receive a third dose for recurrence to undergo safety follow-up for 20 weeks after the third dose of study treatment (Sections 1 and 5.1).
- Added a statement that participating sites will adhere to the relevant safety standards of FACT and JACIE (Section 5.1).
- Added a statement that participants will be approached for enrollment in a long-term registry study (Section 5.3).
- Provided additional guidance on permitted and prohibited medications and the recording of concomitant medications (Section 7.7).

- Updated text such that any participant who develops irreversible, life-threatening, Grade 3 to 4 acute GVHD or a Grade 3 to 4 non-hematologic adverse event between the first and any subsequent dose of posoleucel or placebo that is considered related to study treatment administration should discontinue study treatment (Section 8.1).
- Added the Intent-to-Treat Population; all efficacy endpoints will be analyzed based on the Intent-to-Treat Population, and these analyses will be considered the primary analyses of efficacy (Sections 1, 10.2, and 10.3.1).
- Deleted the Modified Intent-to-Treat Population (Sections 1, 10.2, and 10.3.1).
- Updated the planned analysis of the primary efficacy endpoint to be analyzed based on logistic regression instead of Fisher's exact test. The model will include a term for treatment and, in order to take the randomization stratification variables into account, the following covariates: level of viremia ( $\geq 10,000$  copies/mL or  $< 10,000$  copies/mL AdV DNA) and age ( $\geq 12$  years or  $< 12$  years) (Sections 1 and 10.3.1.1).
- Provided justification for analysis of the primary efficacy endpoint at Day 29 and for durability of response assessments (Section 5.4).
- Added weekly AdV viral load detection in urine for patients with clinical signs and/or symptoms of AdV hemorrhagic cystitis until resolution of hemorrhagic cystitis (Sections 2 and 9.1.1, and Appendix 3).
- Added assessment of coagulation parameters (PT, INR, and PTT) at Days 1 and 29 of the Primary Study Period and Days 1' and 29' of the Cross-Over Period (Section 2 and Appendix 3).
- Provided additional clarification on timing of pregnancy testing relative to study treatment administration on Day 15 and added pregnancy testing to the Week 10 (Week 10'), Week 16 (Week 16'), Week 24 (Week 24'), and ET visits (Sections 2 and 9.3.1; Appendix 3).
- Updated the timing of the first visit of the Cross-Over Period from Week -6' to -1' (Day -42' to -1') to Week -2' to -1' (Day -10' to -1') (Section 2).
- Provided clarification that any evaluations required at the Day -10' to -1' visit of the Cross-Over Period do not have to be repeated if completed within 10 days as part of the Primary Study Period (Section 2).
- Removed the assessment of adenovirus viral load in nasopharyngeal swab from the Day -10' to -1' visit of the Cross-Over Period (Section 2).
- Added an assessment of aGVHD at Day 1 (Day 1') (Section 2).
- Updated language for stool collection to clarify that Screening, Day 1 (Day 1') and Day 29 (Day 29') collection is required for all patients, but collection at other timepoints is required only if the participant has symptoms; however, collection at these other timepoints should be collected in all participants if feasible (Section 2).
- Provided clarity on timing of radiological imaging during the Cross-Over Period (Sections 1, 2, and 9.1.3).

- Provided details on interim analyses and timing of finalizing both the interim analysis SAP and the main SAP relative to conducting interim analyses (Sections 1, 10.3, 10.3.3, and 10.3.4).
- Added additional guidance on post-infusion monitoring (Section 9.3.7).
- Added a statement that all protocol amendments will be submitted to regulatory authorities and ethics committees/IRBs as appropriate (Appendix 2).
- Added a statement that in some jurisdictions, legally effective informed consent must be obtained from all legal guardians for minor patients (Appendix 2).
- Provided guidance on estimating fraction of inspired oxygen (Sections 1 and 6.2; Appendix 9).

Signature Page for P-105-303 Adenovirus Protocol v5.0 30Nov2023

VV-CLIN-000353 v1.0

Approval Task

[REDACTED] 18:14:43 GMT+0000

Approval Task

[REDACTED] 0:00 GMT+0000

Approval Task

[REDACTED] 01:34:10 GMT+0000

Signature Page for P-105-303 Adenovirus Protocol v5.0 30Nov2023

VV-CLIN-000353 v1.0

1 INTRODUCTION

This document details the analysis plan for the study entitled “Phase 3, Randomized, Double-Blind, Placebo-Controlled Trial, with Cross-Over, of Posoleucel (ALVR105) for the Treatment of Adenovirus Infection in Pediatric and Adult Participants Receiving Standard of Care Following Allogeneic Hematopoietic Cell Transplantation”. It is based on Protocol P-105-303 Amendment 4 dated 30 November 2023 and describes the proposed efficacy and safety analyses. Since the study is terminated due to futility, only the primary efficacy endpoint and selected safety endpoints will be analyzed.

The Statistical Analysis Plan (SAP) will be finalized prior to interim database lock. After the database lock, any deviation from the SAP will be documented in the final Clinical Study Report (CSR).

2 STUDY OVERVIEW

2.1 Study Objectives

2.1.1 *Primary Objective*

The primary efficacy objective of this trial is to compare the percentage of participants who have clearance of Adenovirus (AdV) viremia at Day 29 in participants receiving posoleucel and standard of care (SoC) to that in participants receiving placebo and SoC.

The primary safety objective is to determine the safety and tolerability of posoleucel cells by analyzing the incidence and severity of treatment-emergent adverse events (TEAEs), including individual AEs of special interest (AESIs).

2.2 Study Design

2.2.1 *Overview*

This is a Phase 3, multicenter, randomized, double-blind, placebo-controlled study to assess the safety and efficacy of posoleucel as compared to placebo for the treatment of AdV infection in pediatric and adult recipients of HCT with AdV infections receiving SoC.

Approximately 80 participants may be randomized [] to receive [] infusions of posoleucel or placebo []). Randomization will be stratified []

It is expected that no more than 30% of participants, but at least 10% of participants, will be []. Enrollment of participants <1 year of age will occur once preliminary safety data are available from 5 participants ≥ 1 and ≤ 6 years of age. The Data Safety Monitoring Board (DSMB) will review data through Day 29 from these 5 participants once available and make a recommendation. A formal memo will be provided to ethics committees and sites once the DSMB approves enrollment of participants <1 year of age.

The Primary Study Period is 4 weeks (28 days) for evaluation of efficacy, including the primary endpoint, plus 20 weeks for safety follow-up, for a total study duration of 24 weeks. For participants who cross over, the Cross-Over Period is 4 weeks (28 days), plus 20 weeks for safety

[figure not shown]
follow-up. Participants who experience recurrence and receive an additional dose will have safety follow-up for 20 weeks after the final dose.

Participants who progress to active target organ disease or whose existing target organ disease progresses (as assessed by the Investigator and Sponsor Medical Monitor and based on the criteria in Appendix 8 of the protocol) between Day 29 and Week 10 will be considered to have experienced progression and will have the option to be crossed over to the alternate treatment arm. Participants can cross over before Day 29 only if they progress with target organ disease as adjudicated by the Adjudication Committee. Cross-over participants will receive the alternate treatment to which they were originally randomized, posoleucel or placebo [redacted] sequential infusions separated by [redacted] \pm 3 days), but study treatment will remain blinded.

Participants who demonstrate viral clearance by Day 29 of the Primary Study Period but later exhibit a clinically significant recurrence of AdV viremia (i.e., \geq 10,000 copies/mL AdV DNA at the central laboratory) and/or progression of or to active organ disease, will be eligible for an additional dose of the last received therapy (posoleucel or placebo) for recurrence prior to 20 weeks. These participants will continue to have safety follow-up for an additional 20 weeks after administration of the additional dose.

A summary of the study design is shown in [Figure 1](#).

Figure 1. Summary of Study Design

2.2.2 *Method of Treatment Assignment*

Participants who meet all the inclusion criteria and none of the exclusion criteria will be randomized to the study prior to Day 1 of the Primary Study Period. Participants will be randomized [REDACTED] to receive [REDACTED] infusions of posoleucel or placebo. Randomization will be stratified [REDACTED]
[REDACTED]

2.2.3 *Blinding*

The Sponsor designee (e.g., interactive response technology [IRT] vendor) will have a designated randomization administrator who will maintain the randomization codes in accordance with standard operating procedures to ensure the blind integrity is properly maintained. Care should be exercised to ensure that only Sponsor personnel who require knowledge of treatment assignments will be unblinded (e.g., staff involved in suspected unexpected serious adverse reaction (SUSAR) reporting).

An unblinded statistician will be assigned to the DSMB. This statistician will not be involved in any aspects of study conduct outside of the DSMB, and their role will be defined in the DSMB charter.

Unblinding should only occur in the event of an emergency or adverse event (AE) for which it is necessary to know the study treatment to determine an appropriate course of therapy. If the participant's study treatment must be unblinded, the Investigator or qualified designee should contact IRT for the study treatment information. The IRT documentation indicating the blind break at the site must be retained with the participant's source documentation in such a way as to avoid unblinding the treatment assignment to other site or Sponsor blinded personnel.

If possible, the Investigator should attempt to contact the Medical Monitor prior to unblinding in order to get additional information about the study treatment. If not possible, the Investigator should notify the Medical Monitor as soon as possible of the unblinding without disclosing the treatment assignment of the unblinded participant. The Investigator must document the participant's identification, the reason for breaking the blind, and the date and time for breaking the blind.

2.2.4 *Sample Size Determination*

The required sample size is 82 participants based on the below specifications that have received at least 1 dose of posoleucel or PBO.

The sample size was determined based on the following specifications:

1. Superiority study comparing posoleucel plus SoC to placebo plus SoC
2. Primary endpoint is success or failure based on clearance of AdV viremia at Day 29 visit of the Primary Study Period
3. Allocation (posoleucel:placebo) is [REDACTED]
4. Chi-square test
5. Two-sided alpha = 0.05
6. True success rate (defined as clearance of virus) for posoleucel = 0.50
7. True success rate (defined as clearance of virus) for placebo = 0.25
8. Power = 80%

A SSRE and futility analysis will be performed after approximately 40 participants have completed Day 29 of the Primary Study Period. Details of the SSRE and futility analysis will be provided in the SSRE Plan prior to conducting the interim analyses.

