**5.2 Participant and Study Completion**

Approximately 115 participants will be screened to achieve 82 randomly assigned to study treatment and dosed to obtain an estimated total of 41 participants per treatment group evaluable for the primary endpoint.

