## 10 STATISTICAL CONSIDERATIONS

### 10.1 Sample Size Determination

The required sample size is 82 participants based on the below specifications that have received at least 1 dose of posoleucel or PBO.

The sample size was determined based on the following specifications:

1. Superiority study comparing posoleucel plus SoC to placebo plus SoC
2. Primary endpoint is success or failure based on clearance of ADV viremia at Day 29 of the Primary Study Period
3. Allocation (posoleucel:placebo) is █
4. Chi-square test
5. Two-sided alpha = 0.05
6. True success rate (defined as clearance of virus) for posoleucel = 0.55
7. True success rate (defined as clearance of virus) for placebo = 0.25
8. Power = 80%

A SSRE and futility analysis will be performed after approximately 40 participants have completed Day 29 of the Primary Study Period. Details of the SSRE and futility analysis will be provided in the SSRE Plan prior to conducting the interim analyses.

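### The SAP's 82 participants give about 65% power at its stated 50% vs 25% clearance, not 80%; the 82 comes from the protocol's 55% vs 25%

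*SAP*

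**What the plan says.** SAP 2.2.4 (Sample Size Determination) opens with "The required sample size is 82 participants based on the below specifications that have received at least 1 dose of posoleucel or PBO". It then lists a chi-square test, "Two-sided alpha = 0.05", "True success rate (defined as clearance of virus) for posoleucel = 0.50", "True success rate (defined as clearance of virus) for placebo = 0.25" and 80% power. The allocation ratio is blacked out there.

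SAP section 1 says the plan is based on Protocol Amendment 4 of 30 November 2023, which is the protocol version supplied. Protocol 10.1 has the same list with one difference: "True success rate (defined as clearance of virus) for posoleucel = 0.55". The protocol synopsis also has 0.55 and gives the allocation as 1:1. Protocol 5.2 adds the per-arm number: "to obtain an estimated total of 41 participants per treatment group evaluable for the primary endpoint".

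SAP 2.2.1 (Overview) says "Approximately 80 participants may be randomized", whereas the protocol synopsis and section 5.1 say approximately 82.

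**The concern.** Sample size, test, alpha, power and the two success rates are tied together by one formula. If one rate changes from 0.55 to 0.50 and everything else stays, either the sample size or the power must change. In the SAP neither did.

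The SAP is the plan for the abbreviated study report. If its paragraph is carried over, the report will say that the trial was sized for 80% power against a 25-point benefit. Readers of a trial stopped for futility look to the targeted effect to judge what a negative result rules out. Overstating the power for a smaller effect makes the result look more conclusive than the design supports. Amendment 4 also describes its sample-size assumptions as having been made more conservative, so a reader could take 0.50 for a deliberate further step.

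**Working it through.** **Inputs.** Two-sided alpha 0.05 (z = 1.960), power 80% (z = 0.842), placebo rate 0.25, chi-square test: SAP 2.2.4 and Protocol 10.1. Allocation 1:1: protocol synopsis. 41 per arm: Protocol 5.2. No dropout allowance: Amendment 4 rationale, Protocol Appendix 10. Posoleucel rate: 0.55 (protocol) or 0.50 (SAP).

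**Formulas** (pooled variance under the null, no continuity correction), with p̄ the mean of the two rates and d their difference:

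- n per arm = [1.960·√(2p̄(1−p̄)) + 0.842·√(p₁(1−p₁) + p₂(1−p₂))]² / d²
- power = Φ{ [d·√n − 1.960·√(2p̄(1−p̄))] / √(p₁(1−p₁) + p₂(1−p₂)) }

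**Step 1: reproduce the protocol's figure, 0.55 vs 0.25.** p̄ = 0.40 and d = 0.30. The two terms are 1.960·√0.48 = 1.358 and 0.842·√0.435 = 0.555.

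- n = (1.913)² / 0.09 = 40.66, so 41 per arm and 82 in total.
- Power at 41 per arm: (0.30·6.403 − 1.358) / 0.660 = 0.854, and Φ = 80.3%. Exact enumeration of the chi-square test gives 81.7%.

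Both the 82 and the 80% are recovered.

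**Step 2: the same calculation with the SAP's rate, 0.50 vs 0.25.** p̄ = 0.375 and d = 0.25. The two terms are 1.960·√0.46875 = 1.342 and 0.842·√0.4375 = 0.557.

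- n = (1.899)² / 0.0625 = 57.67, so 58 per arm and 116 in total.
- Power at 41 per arm: (0.25·6.403 − 1.342) / 0.661 = 0.391, and Φ = 65.2%. Exact enumeration gives 66.6%.

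The shortfall is about 15 points of power, or 116 − 82 = 34 participants (34/82 = 41% more). Working backwards, the posoleucel rate detectable with 80% power at 41 per arm is 0.549.

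**Step 3: can another method give 82 at 0.50 vs 0.25?**

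| Variant | Total N for 80% power | Power at N = 82 |
|---|---|---|
| Pooled, 1:1, two-sided 0.05 | 116 | 65.2% |
| Continuity correction (power: exact Yates) | 132 | 57.9% |
| Fisher's exact test | not computed | 57.9% |
| Unpooled variance | 110 | 67.7% |
| Arcsine | 116 | 65.9% |
| One-sided 0.025 | 116 | not computed separately |
| One-sided 0.05 | 92 | 76.3% |
| One-sided 0.05, continuity correction | 108 | not computed |
| 2:1 posoleucel:placebo | 132 | 58.7% |
| 1:2 posoleucel:placebo | 129 | 61.8% |

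None does. The blacked-out allocation cannot explain the figure either, since both unequal ratios tried need more participants.

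**Step 4: 80 versus 82.** At 40 per arm, power is 79.3% for 0.55 vs 0.25 and 64.1% for 0.50 vs 0.25, about one point below the values at 41 per arm. This mismatch is small numerically. But the 82 in SAP 2.2.4 counts dosed participants, who are a subset of those randomized, and Amendment 3 reports more randomized-but-untreated patients than expected. A randomized number below 82 therefore cannot supply 82 dosed.

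**The case against.** The arithmetic is not in dispute. The case on the other side is about how much it matters.

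- **Nothing in the analysis uses the figure.** SAP section 1 says the trial was already terminated for futility, and SAP 3.1 says no hypothesis tests will be performed. No population, estimate or interval depends on SAP 2.2.4. This stands, and it confines the consequence to how the design is described.
- **The reported uncertainty comes from elsewhere.** SAP 3.4.2 gives exact 95% confidence intervals for each arm and for the difference. Enrollment at termination is not stated. If it were about 20 per arm, near the planned interim look at about 40 participants (an assumption), fixed-sample power would be about 37% at 0.50 and 49% at 0.55, so neither 80% nor 65% would describe the data in hand. This weakens the argument about conclusiveness. It does not make the design statement correct.
- **The design was adaptive.** Protocol section 10.3.1 (Interim Analyses) allows a sample size re-estimation based on conditional power, so overall power at 0.50 depends on the maximum size in a separate plan that was not supplied. This stands as a limit: the 65% applies to 82 participants without re-estimation. The SAP, however, attaches its 80% to 82.
- **Approximately 80 covers 82.** Fair as to size. It is an editorial point and adds little weight.

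**Conclusion.** The SAP's sample-size statement is wrong as written. With 82 participants (41 per arm, 1:1, chi-square, two-sided 0.05, no dropout allowance, no re-estimation), power at 0.50 versus 0.25 is about 65%, and 80% would need 116. The stated 82 and 80% are reproduced at the protocol's 0.55 versus 0.25.

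The likeliest explanation is a transcription error, because the SAP cites Amendment 4 and its other visible sample-size inputs match that document, but neither document says so. The effect is on the record of the design and on how the futility result may be read, not on any planned estimate.

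**What to change.** In SAP 2.2.4, change the posoleucel success rate to 0.55 so that it agrees with the protocol synopsis and Protocol 10.1. If 0.50 is really intended, keep 82 and restate the power as about 65%, which is less favorable to the trial; nothing in the documents supports that reading. In SAP 2.2.1, replace the approximate 80 randomized with wording that matches 82 dosed.

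If the database is already locked, an erratum or a note in the study report is enough, since SAP section 1 already provides for documenting deviations there. The report should take its design target from the protocol. The cost is a few words, with no extra patients, data or analyses.

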2.3 Study Endpoints

2.3.1 Primary Efficacy Endpoint

The primary efficacy endpoint is the proportion of participants with undetectable viremia (less than lower limit of quantitation [LLOQ]) at Day 29.

2.3.2 Safety Endpoints

The safety endpoint is the incidence and severity of TEAEs, including adverse events of special interest (AESIs), during the study.

The clinical laboratory evaluations (hematology, chemistry, and urinalysis) will also be summarized.

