1. An Early Termination Visit should be performed for any participant who discontinues the study early.
2. Medical history will include diagnosis of underlying disease requiring HCT, underlying disease state at the time of AdV diagnosis, type of donor and cell source of the transplant received, date of HCT, conditioning regimen, CMV serostatus, presence of GVHD, pulmonary function tests, and smoking status.
3. Follicle-stimulating hormone will be tested at screening for women of nonchildbearing potential who are postmenopausal, defined as 12 consecutive months with no menses without an alternative medical cause.
4. A serum pregnancy test will be performed at screening for females of childbearing potential. A serum or urine pregnancy test will be repeated prior to dosing on Day 1 for females of childbearing potential, only if the pregnancy test performed at screening was not completed within 48 hours prior to study treatment administration. A serum or urine pregnancy test will be performed within 48 hours prior to each additional study treatment administration (if applicable) and at the Week 10, Week 16, Week 24, and ET visits for females of childbearing potential. A negative pregnancy test result is required prior to dosing.
5. Participants randomized to the posoleucel group will receive posoleucel cells as an infusion. Participants randomized to the placebo group will receive an IV infusion of [REDACTED] All infusions will be administered IV over approximately [REDACTED] as a slow push. Participants will receive a second dose of blinded study treatment approximately [REDACTED] following the first dose.
6. Includes pain, tenderness, erythema, swelling, and induration. On infusion days, performed pre-dose and at 1 hour post-dose.
7. Participants will be monitored closely and must remain in the clinic for  $\geq 1$  hour after the end of each infusion. Vital signs will be measured at the end of the infusion, and at 15, 30, 45, and 60 minutes after the end of the infusion. Participants must also remain on continuous pulse oximetry for  $\geq 30$  minutes after the end of the infusion. Post-infusion monitoring should be completed for all infusions of study treatment.
8. EQ-5D may be performed up to 24 hours prior to study treatment administration.

9. Includes information on hospital admission and discharge, ICU transfer, oxygen supplementation, and ventilation.

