#### **3.3.2 Potential Risks**

The main potential risks of administration are inflammation at sites of disease or graft versus host disease (GVHD) due to cross reactivity with alloantigens. Adverse events attributable to VST administration may potentially occur in a small percentage of the treated population. These can include both hematologic and non-hematologic effects, as reported in the CHARMS study.

Studies of donor-derived VSTs suggest that VSTs do not persist in patients who receive methylprednisolone in doses of  $\geq 1$  mg/kg/day. Therefore, if participants develop severe inflammatory reactions thought to be attributable to posoleucel, a therapeutic option is to administer methylprednisolone (1 to 2 mg/kg/day). In patients who develop skin rash or skin GVHD, excellent responses have been seen with administration of topical steroids.

As with other biological therapies delivered by IV infusion, possible side effects of posoleucel infusion include allergic reaction (anaphylaxis), decreased oxygenation, nausea/vomiting, arrhythmia, and hypotension.

All participants enrolled in the study (including children) are expected to have venous access catheters in place for both infusion and blood sampling relating to the treatment of their underlying disease and associated HCT procedures. Since study-related collection of blood samples and infusion of study treatment (posoleucel or placebo) will utilize catheters already in place for routine clinical care, there is minimal incremental risk posed by these study-related procedures. A detailed breakdown of the timepoints and blood volumes to be collected during the course of this study is provided in the Laboratory Manual. Since this study will enroll both adult and pediatric participants, there are different sampling schemes (and associated volumes) based on the participant's body weight.

In order to minimize the volume of blood collected during the study, especially for pediatric participants, the blood volume of individual samples has been reduced to the maximum extent feasible wherever possible, and in some cases (eg, pediatric participants weighing <20 kg) collection of blood samples at certain timepoints has been eliminated entirely. This has been done in a manner that is expected to maintain the scientific integrity of the study while minimizing the risks to participants.

4

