#### 10.3.2 Analysis of Safety

Safety will be analyzed and compared between treatment received based on data from the Primary Study Period. In addition, for purposes of complete reporting, safety will be reported for data from the Cross-Over Period by treatment received in the Cross-Over Period, but no comparisons will be made between the two treatments.

The primary safety endpoint is the incidence and severity of TEAEs, including individual AESIs, during the study. The safety profile will be further assessed based on changes in clinical laboratory assessments, vital signs, ECGs, and physical examinations. All safety analyses will be based on the Safety Population.

Safety analyses in general will be descriptive and will be presented by study period (Primary Study Period or Cross-Over Period) and treatment group or cross-over group in a tabular format. Categorical endpoints will be summarized using number and percentage of participants within each category. Continuous endpoints will be summarized descriptively with summary statistics (number of non-missing observations, mean, standard deviation, median, minimum, and maximum).

A TEAE is defined as an adverse event with a start date and time on or after the administration of investigational product or placebo or that worsened in severity after administration of investigational product or placebo through the end of the study. For AEs with a missing start date, the AE will be considered treatment-emergent unless there is additional information indicating that the AE started prior to study treatment. The number and percentage of participants with TEAEs will be tabulated by Medical Dictionary for Regulatory Activities (MedDRA) System Organ Class and Preferred Term for each treatment group/cross-over group. This will be done overall, by severity, and by relationship to treatment. Adverse events leading to discontinuation of the study, SAEs, and AESIs will be summarized by treatment group. By-participant listings will also be provided for any deaths, SAEs, AESIs, and adverse events leading to discontinuation of study drug.

The incidence and severity of acute GVHD during the study, the incidence and severity of chronic GVHD during the study, the incidence and severity of CRS during the study, and the incidence and severity of any treatment-emergent AESIs during the study will each be

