#### Events Meeting the AE Definition

- Any abnormal laboratory test results (hematology, clinical chemistry, or urinalysis) or other safety assessments (eg, electrocardiogram, radiological scans, vital signs measurements), including those that worsen from baseline, considered clinically significant in the medical and scientific judgment of the Investigator (ie, not related to progression of underlying disease).
- Exacerbation of a chronic or intermittent pre-existing condition including either an increase in frequency and/or intensity of the condition.

- New conditions detected or diagnosed after study treatment administration even though it may have been present before the start of the study.
- Signs, symptoms, or the clinical sequelae of a suspected intervention-intervention interaction.
- Signs, symptoms, or the clinical sequelae of a suspected overdose of either study treatment or a concomitant medication. Overdose per se will not be reported as an AE/SAE unless it is an intentional overdose taken with possible suicidal/self-harming intent. Such overdoses should be reported regardless of sequelae.

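### The final SAP names no vital-sign, SpO2 or ECG output, although the protocol commits to these summaries and lists reduced oxygenation, arrhythmia and hypotension as possible infusion effects

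*SAP*

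**What the plan says.** **Risk.** Protocol 3.3.2 states that "possible side effects of posoleucel infusion include allergic reaction (anaphylaxis), decreased oxygenation, nausea/vomiting, arrhythmia, and hypotension".

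**Measurement.** Table 1, footnote 7, of the protocol requires post-infusion monitoring for every infusion: "Vital signs will be measured at the end of the infusion, and at 15, 30, 45, and 60 minutes". It also requires continuous pulse oximetry for at least 30 minutes. Footnote 13 and Protocol 9.3.2 count SpO2 as a vital sign. Footnote 14 places the treatment-day ECG within 1 hour after dosing (the days are redacted). Protocol 7.1.1 requires the monitoring findings to be entered in the eCRF.

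**Protocol analysis.** Section 10.3.2 says: "The safety profile will be further assessed based on changes in clinical laboratory assessments, vital signs, ECGs, and physical examinations". It then specifies summaries of vital signs and of quantitative ECG parameters by visit and treatment group, with change from baseline, and a listing of abnormal physical examination findings. It also says that safety data from the Cross-Over Period will be reported by treatment received.

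**SAP analysis.** The Introduction explains that, because the study was terminated for futility, "only the primary efficacy endpoint and selected safety endpoints will be analyzed". SAP 2.3.2 names TEAEs and AESIs and adds: "The clinical laboratory evaluations (hematology, chemistry, and urinalysis) will also be summarized". Sections 3.5.1 to 3.5.3 cover adverse events, AESIs and laboratory tests, and nothing else.

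**The concern.** The SAP retains the primary safety objective, which is the safety and tolerability of posoleucel. For the infusion itself, the protocol names specific physiological risks and schedules measurements that would show them. If those measurements are not tabulated, the report depends on what the sites recorded as adverse events.

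That route has a threshold. Under Appendix 4 an abnormal ECG or vital sign is an adverse event when "considered clinically significant in the medical and scientific judgment of the Investigator". The same appendix excludes abnormal assessments linked to the underlying disease unless they are worse than expected. Exclusion criterion 7 allows enrolment on supplemental oxygen up to an FiO2 of 0.5, so a fall in saturation after an infusion could be put down to existing lung disease. A modest but systematic shift on active treatment could therefore be measured, entered in the database and never shown, in a blinded placebo-controlled comparison of a cell therapy given mainly to children.

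**Working it through.** No formula applies; the check compares the two documents measure by measure.

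| Measure | Protocol 10.3.2 | Output named in the SAP |
|---|---|---|
| TEAEs and AESIs | Tables and listings | Yes (3.5.1, 3.5.2) |
| Laboratory tests | By visit and group, with change from baseline | Yes (3.5.3), Primary Study Period |
| Vital signs, including SpO2 | By visit and group, with change from baseline | None |
| ECG | By visit and group, with change from baseline | None; the term survives only in the abbreviation list |
| Physical examination | Listing of abnormal findings | None |

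1. The protocol names four supportive measures beyond adverse events. The SAP keeps one, so 4 − 1 = 3 have no specified output.

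2. The SAP's visit windows (Appendix 1) cover viral load and clinical laboratory data only. This agrees with the absence of any by-visit table for vital signs or ECG.

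3. The listings named in SAP 3.5.1 and 3.5.3 are for adverse events and selected laboratory data.

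4. For the Cross-Over Period, the only safety tabulation in SAP 3.5 is of AESIs (3.5.2). Placebo participants who cross over receive posoleucel infusions in that period.

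5. What the protocol's own tables would have shown differs by measure:
   - *Vital signs.* Table 1, footnote 11, places the treatment-day visit measurement before dosing. A by-visit table would naturally use that value. Section 10.3.2 makes no explicit provision for the timed post-infusion readings, of which there are 5 per infusion, or 5 × 2 = 10 per participant given both infusions of a period.
   - *ECG.* The treatment-day ECG is taken after dosing, so the by-visit table would have compared a post-infusion tracing with baseline. Table 1 marks one earlier ECG, at screening, and SAP 3.1.3 defines baseline as the last value before the first dose. The comparison is therefore with screening, not with a same-day pre-dose tracing.

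6. Post-infusion SpO2 is less certain than the other readings. Protocol 9.3.7 lists the timed measurements as temperature, heart rate, respiration rate and blood pressure, without SpO2. Oximetry is continuous for at least 30 minutes, but no recording times are given. Whether serial SpO2 values are in the database cannot be settled from the documents.

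**The case against.** The strongest reply is that this is a disclosed scope decision. The SAP ties the reduction to futility, and its signature page labels it as written for an abbreviated report. The primary safety endpoint is intact: TEAEs by severity, AESIs, infusion-related events and CRS grades are all tabulated. This stands, and it limits the weight of the point. It does not explain the selection: the SAP neither names the dropped measures nor says why laboratory data stay while vital signs and ECG go.

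The documents do not support several stronger readings that a reader might infer:

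- *That the SAP cancelled a planned analysis of the 0 to 60 minute readings.* Protocol 10.3.2 promised by-visit vital-sign summaries only, so a table of those readings would be an addition.
- *That these are the trial's sole objective data on acute infusion harm.* Infusion sites are examined before and 1 hour after each dose. CRS grades are built from blood-pressure support and oxygen-delivery criteria, although fever is normally required.
- *That the values cannot appear anywhere.* SAP 3.1 says in general terms that collected data will be presented in tables and listings, so a listing is not ruled out.
- *That the trial could detect a given SpO2 difference.* The documents give no variability for such a change and do not clearly provide timed SpO2 readings. The SAP also plans no hypothesis tests.

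The remaining defence is that adverse-event reporting captures whatever matters clinically. That holds only in part. Infusion-related events have no definition or time window in either document, since the protocol's AESI section points to grading criteria for GVHD and CRS only.

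**Conclusion.** The point holds as a gap between protocol and SAP. Vital signs including SpO2, and ECG, have committed summaries in Protocol 10.3.2 and no named output in the SAP; the physical examination listing is missing too. What is lost is any measured change that the investigator did not judge clinically significant, including changes after posoleucel infusions in the Cross-Over Period. The size is three of four supportive measures without a specified output. No effect on a trial conclusion can be quantified from the documents.

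This rests on two assumptions: that the SAP text is the full list of planned outputs (table shells were not available), and that the post-infusion readings were entered in the eCRF as Protocol 7.1.1 requires. The change should be made because it is cheap and supports the retained primary safety objective. The omission does not invalidate the safety analysis.

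**What to change.** In SAP 3.5:

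1. Restore the vital-sign and ECG tables of Protocol 10.3.2, by actual treatment and visit, with change from baseline as defined in SAP 3.1.3. State the visit assignment for them, since Appendix 1 has no windows for these data.
2. Add one descriptive table by actual treatment and infusion number, for the Primary and Cross-Over Periods, of each participant's largest change from the pre-infusion value among the post-infusion readings held in the eCRF: heart rate, blood pressure, and SpO2 where recorded. Using within-participant change makes it reasonable to show children and adults together.
3. Provide by-participant listings for both periods, and either restore the physical examination listing or state that it is omitted and why.

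No test or p-value is needed. If the tables are judged too much for an abbreviated report, the minimum is to name the omitted measures, give the reason and supply the listings. The cost is modest programming on data already collected. No procedure, monitoring rule or dosing rule changes.
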